2.6.2 Handling of missing values for secondary endpoints

Missing data during study follow up will be imputed following the same principles as for the primary estimands/endpoints: intermittent missing data will be imputed according to the missing at random (MAR) principle. Missing data due to withdrawal from the study or discontinuation for iptacopan treatment will be imputed by recovering a return to pre-treatment levels. This would be implemented by imputing missing values from a normal distribution with mean and standard deviation derived from all baseline values. In case of intermittent missing data, their missing data will be handled with a missing at random approach and imputed consequently.

The model for imputation will be Markov chain Monte Carlo (MCMC) method, and only baseline values will be included in the imputation model.

For the transfusion avoidance endpoint the handling of missing data will be very similar to the handling of missing data for the primary endpoints and the same multiple imputed datasets can be used.

For the specific case of missing hemoglobin due to withdrawal, the imputation will reflect whether or not data were missing following a transfusion.

In the case of definitive withdrawal of study follow up following a transfusion only hemoglobin levels at visits during 30 days following the transfusion and until treatment discontinuation would be imputed under the MAR assumption. The missing hemoglobin after treatment discontinuation will be imputed by recovering a return to pre-treatment levels of hemoglobin. This would be implemented by imputing missing values from a normal distribution with mean and standard deviation derived from all baseline values. More specifically a patient should be first imputed in the hypothetical scenario for hemoglobin until end of treatment. In case of definite withdrawal of study follow up without transfusion missing data will be imputed as stated in [Section 2.5.3](#).

In all estimation based on a longitudinal model, missing data will be imputed multiple times. The imputed datasets will be used in the estimation of the longitudinal model. Where both intercurrent events (as for the hypothetical estimand estimating hemoglobin levels) and missing data are imputed or where only missing data are imputed, the model estimation will be derived using Rubin's combination rules.

For endpoints, eg. FACIT-fatigue which are constrained to be in a finite range of values, if some imputed values are lower than the limit, then they will be truncated to the lower limit and if some imputed values exceed the upper limit then they will be truncated to the upper limit.

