1.2.2 Secondary estimands

The population associated with the secondary estimands is the same as for the primary estimands. For these secondary estimands we consider the same intercurrent events as for the primary estimands. The proposed approach in the case of transfusion handling will be described in the endpoint definition, while discontinuations of study medication, breakthrough hemolysis events, and MAVEs whose impact is expected to be reflected in the respective endpoints, will be handled with a treatment policy strategy.

The secondary estimands are defined by the evaluation of treatment effect on the following endpoints and summary measures:

- Response defined as having Hb levels ≥ 12 g/dL between Day 126 and Day 168 in absence of red blood cell transfusion between Day 14 and Day 168. The summary measure is the same as for the primary endpoint.
- Absence of administration of packed red blood cell transfusions (pRBC) between Day 14 and Day 168. Proportions of participants not receiving any transfusions between Day

14 and Day 168 (Transfusion Avoidance). The summary measure is the same as for the primary endpoint.

- Changes from baseline in hemoglobin between Day 126 and Day 168 where transfusions occurring between Day 14 and Day 168 are treated within a hypothetical strategy (as if the participants had not received any transfusions). The summary measure is the mean change from baseline in hemoglobin levels assessed between Day 126 and Day 168.
- Percent change from baseline in LDH between Day 126 and Day 168 where the strategy applied to transfusions is treatment policy. The summary measure is derived from the mean log transformed ratio to baseline in LDH between Day 126 and Day 168.
- Rates of BTH occurring between Day 1 and Day 168. The summary measure is occurrences per year.
- Change from baseline in reticulocytes counts between Day 126 and Day 168 where the strategy applied to transfusions is treatment policy. The summary measure is the mean change from baseline in reticulocytes counts assessed between Day 126 and Day 168.
- Change from baseline in scores of fatigue using the FACIT Fatigue questionnaire between Day 126 and Day 168, where the strategy applied to transfusions is treatment policy. The summary measure is the mean change from baseline in scores of fatigue assessed between Day 126 and Day 168.
- Rates of Major Adverse Vascular Events (MAVE) occurring between Day 1 and Day 168. The summary measure is occurrences per year.

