2.5.1 Primary endpoint(s)/Primary estimand(s)

The primary endpoint defines the response as sustained increase in hemoglobin and a participant as a responder if :

- The change from baseline in hemoglobin is ≥ 2 g/dL on three out of four measurements taken at the visits occurring in last six weeks (from Day 126 to Day 168) of the Core treatment period, and
- The participant has not met the criteria for administration of RBC transfusions nor received a transfusion between Day 14 and Day 168.
- The baseline hemoglobin will be the mean of the two measurements taken during screening that confirm the hemoglobin entry criterion in patients who do not receive a transfusion between the first and second confirmatory measurement. In patients who receive a transfusion after the first confirmatory hemoglobin measurement, the baseline will be the first measurement.

Criteria for administration of RBC transfusions

To standardize criteria for administration, transfusion criteria have been established and will apply starting from Day 1 of the study.

Packed-RBC transfusions will be administered to participants in the following cases:

- Hemoglobin level of ≤ 9 g/dL (≤ 8 g/dL for Chinese population) with signs and/or symptoms of sufficient severity to warrant a transfusion
- Hemoglobin of ≤ 7 g/dL (≤ 6 g/dL for Chinese population), regardless of presence of clinical signs and/or symptoms

The transfusions information will be collected on the 'Transfusion-during the study' CRF page.

Handling of intercurrent events of primary estimand

Reaching the protocol established criteria for RBC transfusions will be handled using a composite strategy for primary endpoint.

Intercurrent events stemming from discontinuation of treatment, breakthrough hemolysis events and MAVEs, expected to be reflected in the endpoint, will be handled with a treatment policy strategy.

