The primary analysis of primary endpoint is the assessment of the proportion of patients reaching the status of responder (as defined in [Section 2.5.1](#)). The lower bound of the two-sided 95% confidence interval of the response rate obtained from primary analysis will be compared to a threshold of 15%. Lower bound of the two-sided 95% confidence interval $\geq 15\%$ is sufficient for demonstration that iptacopan improves hematological response in PNH patients with hemolysis and anemia in the absence of transfusions. The derivation of the threshold is explained in [Section 5.2.2.3](#).

2.5.3 Handling of missing values not related to intercurrent event.

For the primary response definitions, RBC transfusion will qualify the participant as a non-responder, hence missing hemoglobin data after meeting the criteria for transfusion or after receiving a transfusion during Day 14 to Day 168 does not impact the primary analysis.

Missing hemoglobin data due to withdrawal from study in the core treatment period in the event that a participant did not have a prior RBC transfusion, will be imputed in a multiple imputation framework based on pattern mixture models. This aims to be consistent with the inclusion of hemoglobin data under the treatment policy strategy following all other intercurrent events. The need for transfusion will then be derived from this imputation with imputed values ≤ 9 g/dL (≤ 8 g/dL for Chinese population) considered sufficient to warrant a transfusion. This means assuming conservatively that all patients with imputed hemoglobin between 9 g/dL and 7 g/dL (between 8 g/dL and 6 g/dL for chinese patients) would have presented symptoms warranting transfusion.

- For participants withdrawing from study after discontinuation of iptacopan, the model implemented will recover a return to pre-treatment levels of Hb. This would be implemented by imputing missing values from a normal distribution with mean and standard deviation derived from all baseline hemoglobin values.
- For participants with intermittent missing data, their missing data will be handled with a missing at random approach and imputed consequently.

The model for imputation will be Markov chain Monte Carlo (MCMC) method and only baseline hemoglobin will be included in the imputation model.

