2.6.1.3 Change from baseline in hemoglobin levels

Estimation of change from baseline in hemoglobin levels is under the hypothetical situation in which participants would not have received transfusions on iptacopan treatment. For this analysis, if a participant had a transfusion during the core treatment period then the hemoglobin values 30 days following the transfusion will be considered missing and hemoglobin data will be imputed. In practice, this would be implemented considering participants on iptacopan to have data imputed assuming missing at random. This will be accomplished by the use of imputed values ([Section 2.5.3](#)).

The model for the estimation is a mixed model for repeated measures (MMRM) considering an unstructured covariance structure. The model will include transfusion dependence, age (indicator of age ≥ 45 years), sex, visit, baseline hemoglobin and the interactions between visits and baseline levels. The treatment estimates will be computed as the mean changes from baseline corresponding to the average of hemoglobin levels measured in the last 6 weeks of treatment (that is the visits occurring between Day 126 and Day 168).

The estimated least square mean estimate of the treatment effect and the associated 95% confidence interval will be plotted over time. Refer to [Section 5.2.3](#) for detail.

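### Followed to the letter, the baseline-only imputation rule biases the secondary mean hemoglobin change upward; the SAP should state that the on-treatment visit values enter the model

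*SAP*

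**What the plan says.** The secondary estimand for change in Hb asks for the mean change over Day 126 to Day 168 "as if the participants had not received any transfusions" (SAP 1.2.2). To estimate it, SAP 2.6.1.3 says that after a transfusion "the hemoglobin values 30 days following the transfusion will be considered missing and hemoglobin data will be imputed". It adds that "this would be implemented considering participants on iptacopan to have data imputed assuming missing at random", and for the method it refers to SAP 2.5.3: "This will be accomplished by the use of imputed values".

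SAP 2.5.3 names MCMC and says that "only baseline hemoglobin will be included in the imputation model". SAP 2.6.2 repeats this for all secondary endpoints: "only baseline values will be included in the imputation model". For participants who withdraw after a transfusion, SAP 2.6.2 says that "only hemoglobin levels at visits during 30 days following the transfusion and until treatment discontinuation would be imputed under the MAR assumption"; later values are drawn from the baseline distribution.

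Transfusion depends on current Hb (SAP 2.5.1). It is given at 9 g/dL or below with sufficiently severe symptoms, and at 7 g/dL or below "regardless of presence of clinical signs and/or symptoms". The cut-offs are 8 and 6 g/dL for Chinese participants.

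Protocol 12.5.1 describes another method for the same values: normal draws with the mean confined to a range compatible with no transfusion, and a covariance taken from the observed within-participant matrix. SAP Section 4 lists one departure from the protocol, the timing of the transfusion-dependence indicator.

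**The concern.** Missing at random holds only relative to what the imputation model conditions on. The deleted values belong to participants whose on-treatment Hb was low enough to trigger a transfusion. Given that earlier low Hb, the deletion is ignorable or nearly so. Given baseline alone it is not: a poor responder receives the value of an average responder with the same baseline, and the mean change is pushed up. The trial has one arm, so no comparison cancels the error.

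No planned analysis isolates this. For Hb change, the sensitivity analysis in SAP 2.6.3 swaps in local laboratory values, and the supportive analysis in SAP 2.6.4 uses a treatment-policy strategy, which answers a different question. The supportive hypothetical analyses of LDH, FACIT-Fatigue and reticulocytes (SAP 2.6.4) follow SAP 2.6.2 and so inherit the same sentence; no size was computed for them.

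**Working it through.** **Plan's own figure.** There is none for this endpoint. The 96.4% probability in the sample-size section concerns the primary endpoint and has no bearing here.

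**Inputs from the documents.** N = 40; 11 post-baseline core visits (Day 7 to Day 168, protocol Table 8-1); non-Chinese transfusion triggers; deletion for 30 days after a transfusion; estimation window Day 126 to 168.

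**Assumed inputs (not in the documents).** Baseline Hb 8 g/dL (SD 1, kept below 10); mean gain 4, 3, 2 or 1 g/dL, approached with a time constant of 21 days; between-participant SD of gain 0.9 or 1.5; visit SD 0.7; measured baseline the average of two values; probability p of qualifying symptoms at a visit with Hb of 9 or below, 0.1 or 0.3.

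**Scale.** The standard error of the mean change is √[(SD² + 0.7²/4 + 0.7²/2)/40]:
- SD 0.9: √[(0.81 + 0.1225 + 0.245)/40] = 0.17 g/dL.
- SD 1.5: √[(2.25 + 0.1225 + 0.245)/40] = 0.26 g/dL.

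**Literal reading.** Each visit is regressed on baseline only. Bias is the mean change after imputation minus the known untransfused mean change. In (A) no new transfusion occurs within 30 days of the last. In (B) repeats are allowed, and each transfusion raises Hb by 2 g/dL, fading over 30 days. Ranges run over the four combinations of SD and p.

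| True gain (g/dL) | Transfused from Day 14 in (A), of 40 | Bias in (A) | Bias in (B) |
|---|---|---|---|
| 4 | 2–6 | +0.007 to +0.075 | +0.009 to +0.092 |
| 3 | 5–11 | +0.027 to +0.166 | +0.029 to +0.205 |
| 2 | 11–18 | +0.072 to +0.259 | +0.096 to +0.389 |
| 1 | 19–27 | +0.141 to +0.385 | +0.221 to +0.668 |

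With p = 0.6 in (B), the bias is +0.037 (SD 0.9) to +0.137 (SD 1.5) at a gain of 4, and +0.491 to +0.906 at a gain of 1.

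**All visits in a joint normal model.** In (A) the bias is −0.003 to +0.004. In (B) it is +0.001 to +0.006 at a gain of 4, but +0.043 to +0.149 at a gain of 1, because some triggers then depend on values that were themselves deleted.

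**Second simulation, different assumptions.** 20,000 participants per scenario, baseline 8.2 (SD 1.1), mean change 2.5 to 4.5, response SD 1.3 to 1.6, visit SD 0.5, symptom probability 0.3 or 0.8, and correlation of baseline with plateau Hb 0.3 or 0.85 (the range in SAP 5.2.2.3). The literal reading was biased upward in all 20 scenarios, by +0.002 to +0.259. The joint model gave −0.001 to +0.001.

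The mechanism can be checked by hand: bias = share of window values deleted × (imputed mean − true untransfused mean of those values).
- Mean change 4.0, symptom probability 0.3, correlation 0.3: 0.010 × (11.93 − 8.88) = +0.031.
- Mean change 2.5, symptom probability 0.8, correlation 0.3: 0.114 × (10.83 − 8.56) = +0.259.

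**The case against.** The strongest reply is that MCMC imputation models jointly the variables it fills in. A model holding nothing but baseline could impute no visit value, so the sentence may well mean that baseline is the only covariate added to the repeated values, leaving out the age, sex and transfusion-dependence terms of the analysis model. That is a reasonable reading, and on it the bias nearly vanishes. It stands as a limit on the point but does not remove it: the SAP does not choose between the readings, both sections use the word 'only', and the amendment history says detail was added there for implementation.

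Three further limits stand. The larger biases arise where the drug works poorly and many participants are transfused. The Chinese cut-offs are lower, so fewer values would be deleted. And the treatment-policy repeat in SAP 2.6.4, though not a test of the imputation model, would give some warning if the hypothetical mean came out close to it or above it.

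Return-to-pre-treatment imputation pulls the mean change down, but it applies to values missing after withdrawal or discontinuation and does not correct this error.

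A reader might infer that the plan certainly inflates the Hb result, or that the primary conclusion is at risk. The documents support neither. The first depends on an unresolved reading. As to the second, a participant who is transfused or meets the criteria between Day 14 and Day 168 is already a non-responder, whatever is imputed. For other missing visits, one simulation (gain of 4, 10% missing one window visit) put the literal rule's extra loss at 0.19 − 0.13 = 0.06 to 0.69 − 0.15 = 0.54 percentage points of response, which is conservative.

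Nor does the omission from SAP Section 4 show bias. The protocol never defines its range, so the SAP had to settle on something workable.

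**Conclusion.** The point holds as a wording fault with a modest numerical consequence. On the literal reading, the secondary mean Hb change is overstated by about +0.01 to +0.09 g/dL for a true gain of 4, +0.03 to +0.2 for 3, and +0.07 to +0.4 for 2. For gains of 4 and 3 that is below one standard error in each main scenario. At a gain of 2 it can exceed one standard error if responses vary widely and transfusions repeat within 30 days. It is larger only if the drug works poorly or if symptoms lead to transfusion more often than assumed.

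On the other reading the bias is near zero, apart from a residual of up to about +0.15 g/dL at a gain of 1 with repeat transfusions. The direction follows from the transfusion triggers; the sizes rest on the assumed inputs above. The estimate carries no success threshold, and the 15% criterion for the primary endpoint is essentially unaffected.

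**What to change.** In SAP 2.5.3 and 2.6.2, replace the sentence with: *The MCMC imputation model contains the baseline value and all scheduled post-baseline values of the endpoint; no other covariates are added.* Add that a ridge prior, with its value stated in advance, is used if the covariance matrix is near-singular.

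The cost is wording and minor imputation code, with no new data. For Hb the model is larger: 12 variables have 12 × 13/2 = 78 variances and covariances, estimated from 40 participants, which is why the ridge prior is needed as a fallback. If the literal rule has already been programmed, the reported Hb change may become slightly less favorable.

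As a documentation item only, list in SAP Section 4, with a reason, that the restricted-mean imputation of protocol 12.5.1 is replaced by 30-day deletion with imputation under missing at random. This changes no result.

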2.6.3 Sensitivity analyses

Sensitivity analyses will be performed where missing central lab data will be replaced by available local lab data collected at the same visit. MMRM for analysis of change from baseline in hemoglobin under a hypothetical strategy, change from baseline in reticulocytes, and change from baseline in LDH levels stated in [Section 2.6.1.1](#), [2.6.1.2](#), [2.6.1.3](#), [2.6.1.5](#), [2.6.1.6](#), respectively, will be performed.

Additional sensitivity analyses will be performed for hemoglobin normalization ([Section 2.6.1.1](#)) and transfusion avoidance ([Section 2.6.1.2](#)):

- Considering the need for transfusion derived from imputation with imputed values ≤ 7 g/dL (≤ 6 g/dL for Chinese population) to be sufficient to warrant a transfusion.
- Considering administered transfusions.

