8.3.3 Breakthrough hemolysis

The occurrence of BTH will be monitored continuously during the Core treatment period.

The criteria for clinical breakthrough is defined in [Table 8-3](#) below if either one of the two clinical criteria is met, in presence of the laboratory evidence of intravascular hemolysis and should be reported in the 'Breakthrough hemolysis' CRF page in addition to the AE page.

In contrast to clinical breakthrough as defined, the isolated laboratory evidence of increased intravascular hemolysis, without meaningful decrease in hemoglobin and without other clinical signs or symptoms of hemolysis (per [Table 8-3](#)) is defined as subclinical breakthrough hemolysis, and should **not** be reported in the 'Breakthrough hemolysis' CRF page.

Table 8-3 Breakthrough hemolysis definition

	Clinical criteria		Laboratory criteria
	Hemoglobin levels	Signs or symptoms	LDH level
Clinical breakthrough*	Decrease equal to or more than 2 g/dL (compared to the latest assessment, or within 15 days)	Gross hemoglobinuria, painful crisis, dysphagia or any other significant clinical PNH-related signs & symptoms	> 1.5-times ULN and increased as compared to the last 2 assessments
Subclinical breakthrough	Decrease less than 2 g/dL (compared to the latest assessment, or within 15 days)	No clinical signs or symptoms, except moderate hemoglobinuria	> 1.5-times ULN and increased as compared to the last 2 assessments

LDH: lactate dehydrogenase; ULN: Upper Limit of Normal;

*The breakthrough is defined clinical if either one of the two clinical criteria is demonstrated, in presence of laboratory evidence of intravascular hemolysis (LDH level)

During the Extension treatment period, breakthrough hemolysis will be monitored continuously until the end of study visit following the same criteria and guidance described above.

The assessment could be based on local laboratory results. However, the investigator should also collect at the same time a sample for the central laboratory assessment of hemoglobin and LDH, whenever possible.

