1.2 Study objectives and endpoints

Table 1-1 Objectives and related endpoints for the Core treatment period

Objective(s)	Endpoint(s)
Primary Objective(s)	Endpoint(s) for primary objective(s)

 To assess the effect of iptacopan on proportion of participants treated with iptacopan achieving a sustained increase from baseline in hemoglobin levels of ≥ 2 g/dL in the absence of red blood cell transfusion 	
 Response defined as having an increase from baseline in Hb ≥ 2 g/dL assessed between Day 126 and Day 168, in the absence of packed red blood cell (pRBC) transfusions between Day 14 and Day 168
Secondary Objective(s)	Endpoint(s) for secondary objective(s)

 To assess the effect of iptacopan on the proportion of participants achieving 	
 Response defined as having Hb levels ≥ 12 g/dL between Day 126 and Day 168 in

Objective(s)	Endpoint(s)
sustained hemoglobin levels \geq 12 g/dL in the absence of red blood cell transfusions	absence of red blood cell transfusion between Day 14 and Day 168

 To assess the effect of iptacopan on transfusion avoidance (TA) defined as the proportion of participants who remain free from transfusions 	
 Absence of administration of packed-red blood cell transfusions between Day 14 and Day 168

 To assess the effect of iptacopan on average change in hemoglobin 	
 Change from baseline in hemoglobin (g/dL) as mean of visits between Day 126 and Day 168

 To assess the effect of iptacopan on average percent change in Lactate Dehydrogenase (LDH) 	
 Percent change from baseline in LDH levels (U/L) as mean of visits between Day 126 and Day 168

 To assess the effect of iptacopan on the rate of breakthrough hemolysis (BTH) 	
 Occurrences of breakthrough hemolysis reported between Day 1 and Day 168

 To assess the effect of iptacopan on average change in reticulocyte counts 	
 Change from baseline in reticulocyte counts ($10^9/L$) as mean of visits between Day 126 and Day 168

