2.1.1.2 Baseline definition

For the analysis on efficacy and safety data in the core treatment period on the analysis sets FAS and SAF as defined in [Section 2.2](#), the baseline value is defined to be the last result obtained at or prior to start of study treatment (Day 1) for baseline demographics, medical history, lab values, vital signs and ECGs. Most variables will have their baseline at Day 1, unless otherwise specified. For assessments not performed at Day 1, the assessment at the screening visit or most recent assessment prior to start of study treatment will be used as baseline. For baseline derivation of laboratory parameters, central lab measurements will be used. If there are no central lab data available, then local lab measurements will be used for baseline computations only.

- The baseline hemoglobin will be the mean of the two confirmatory measurements (planned) taken during screening that confirm the hemoglobin entry criterion in patients who do not receive a transfusion between the first and second confirmatory measurement. In patients who receive a transfusion after the first confirmatory measurement, the baseline will be the first measurement.

If there is only one confirmatory measurement but additional unplanned measurements taken during screening, for patients who do not receive transfusion in the screening, then the mean of the first measurement and the second measurement taken within 2 to 8 weeks after the first measurement will be considered to be the baseline. In patients who receive a transfusion after the first measurement, the baseline will be the first measurement. For patients with transfusion on same day, but hemoglobin measurement taken before transfusion, the baseline hemoglobin should be the average of the measurements considering the hemoglobin measurement before transfusion.

- The baseline score of fatigue using the FACIT-Fatigue questionnaire will be defined as the mean of first assessment prior to Day 1 and the Day 1 value. [REDACTED]
- The baseline LDH will be defined as the value on Day 1 (prior to starting treatment). If Day 1 value is not available, then the mean of two screening/LDH confirmatory values will be used. If screening value is not available, the baseline LDH will be defined as single confirmatory LDH value.

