2.5 Analysis of the primary objective

For all efficacy analyses based on laboratory data (e.g. hemoglobin, reticulocytes etc.) addressing primary and secondary objectives, the information obtained from the central lab will be used.

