2.6.1.6 Percent change from baseline in LDH

The treatment effect on percent change from baseline in LDH will be assessed using a MMRM of log transformed ratio to baseline based on all observations collected during follow-up. The model for the estimation is a MMRM considering an unstructured covariance structure. The model will include transfusion dependence, age (indicator of age ≥ 45 years), sex, visit, log-transformed baseline LDH and the interactions between visits and log-transformed baseline levels. Estimation will be derived based on the average of the log transformed ratio from baseline estimated between Day 126 and Day 168. Percentage change from baseline (reduction or increase) and associated 95% confidence intervals will be plotted for treatment effect over time.

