Secondary estimand 4	Change from baseline in scores of fatigue using the FACIT Fatigue questionnaire**	Treatment policy Missing data on iptacopan after study discontinuation imputed using "return to pre-treatment"	Treatment policy	Treatment policy	Treatment policy	Mean change from baseline in FACIT fatigue scores
Supportive analysis (Secondary) 4.1	Change from baseline in scores of fatigue using the FACIT Fatigue questionnaire**	Treatment policy Missing data on iptacopan after study discontinuation imputed using "return to pre-treatment"	Treatment policy	Treatment policy	Hypothetical Policy	Mean change from baseline in FACIT fatigue scores
Secondary estimand 5	Change from baseline in reticulocytes counts**	Treatment policy	Treatment policy	Treatment policy	Treatment policy	Mean change from baseline in reticulocyte counts
Sensitivity analysis (Secondary) 5.1	Change from baseline in reticulocytes counts**	Treatment policy Missing reticulocyte central lab data replaced by local lab data at same visit.	Treatment policy	Treatment policy	Treatment policy	Mean change from baseline in reticulocyte counts

Estimand	Endpoint	Handling strategy of intercurrent events				Summary measure
		Missing data on iptacopan after study discontinuation imputed using "return to pre-treatment"				
Supportive estimand (Secondary) 5.1	Change from baseline in reticulocytes counts**	Treatment policy	Treatment policy	Treatment policy	Hypothetical Policy	Mean change from baseline in reticulocyte counts
Secondary estimand 6	Percent change from baseline in LDH**	Treatment policy Missing data on iptacopan after study discontinuation imputed using "return to pre-treatment"	Treatment policy	Treatment policy	Treatment policy	The log transformed LDH ratio to baseline
Sensitivity analysis 6.1	Percent change from baseline in LDH**	Treatment policy Missing LDH central lab data replaced by local lab data at same visit. Missing data on iptacopan after study discontinuation imputed using "return to pre-treatment"	Treatment policy	Treatment policy	Treatment policy	The log transformed LDH ratio to baseline
Supportive estimand (Secondary) 6.1	Percent change from baseline in LDH**	Treatment policy Missing data on iptacopan after study discontinuation imputed using "return to pre-treatment"	Treatment policy	Treatment policy	Hypothetical Policy	The log transformed LDH ratio to baseline

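### The LDH sensitivity analysis fills missing central values with local values in U/L without scaling, so it can pick up a change of laboratory

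*SAP*

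**What the plan says.** **LDH endpoint.** SAP 1.2 defines it as "Percent change from baseline in LDH levels (U/L) as mean of visits between Day 126 and Day 168". SAP 2.6.1.6 analyses it with an "MMRM of log transformed ratio to baseline based on all observations collected during follow-up". For the efficacy analyses based on laboratory data, SAP 2.5 says that "the information obtained from the central lab will be used".

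**Sensitivity analysis.** SAP 2.6.3: "Sensitivity analyses will be performed where missing central lab data will be replaced by available local lab data collected at the same visit". LDH is one of the endpoints listed there, and Table 5-1, row 6.1, repeats the rule: "Missing LDH central lab data replaced by local lab data at same visit". Neither place mentions conversion, scaling by ULN or a check that the laboratories agree.

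**Where local values come from.** Protocol 8.4.1 makes central testing the default but permits a local laboratory when a participant cannot attend. Protocol 8.6 has off-site samples shipped to the central laboratory and provides local-laboratory CRF pages for results obtained locally.

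**Breakthrough hemolysis (BTH).** Protocol Table 8-3 requires LDH "> 1.5-times ULN and increased as compared to the last 2 assessments", together with a clinical criterion. Of local testing, Protocol 8.3.3 says: "The assessment could be based on local laboratory results". It also asks for a paired central sample whenever possible. SAP 2.6.1.8 counts the clinical events entered on the BTH CRF page.

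**The concern.** A ratio to baseline cancels the laboratory's scale only if numerator and denominator come from the same laboratory. In row 6.1 the numerator can be local while the baseline is central. If the local laboratory reads k times the central one on the same blood, each substituted visit carries an extra ln(k) that has nothing to do with treatment.

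Row 6.1 exists to show whether the LDH result depends on how missing central values are handled. The main analysis imputes those values; row 6.1 replaces them with something measured. If the two results differ, the reader needs to know whether the imputation was wrong or the laboratories disagree. As specified, the analysis cannot tell these apart. It could suggest fragility where there is none, or hide a real difference.

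The BTH criterion raises a related but separate question. Its threshold is relative to ULN, but the comparison with the two previous assessments names neither a unit nor a laboratory.

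**Working it through.** The plan gives no figure for this point, so there is none to reproduce. What follows is an illustration of size.

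**Inputs**
- True ratio to baseline R = 0.40, a 60% fall. Protocol 4.2 reports that every participant in a Phase 2 interim analysis had a reduction of more than 60%, so this is a round illustrative value.
- k = local reading / central reading on the same blood. Not in the documents; assumed 0.8 to 2.0.
- f = share of Day 126 to Day 168 LDH values that are local. Not in the documents; assumed 5% and 20%.
- Four visits in the window (Days 126, 140, 154 and 168; Protocol Table 8-1).

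**Formulas.** A substituted visit shifts the log ratio by ln(k). Averaging over the window:
- group: apparent change = R × exp(f × ln k) − 1
- one participant with m of 4 local visits: apparent change = R × k^(m/4) − 1

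Example, k = 2.0 and f = 0.20: 0.40 × 2^0.20 − 1 = 0.40 × 1.149 − 1 = −54.1%.

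| k | Group, 5% local | Group, 20% local | Participant, 1 of 4 local | Participant, 4 of 4 local |
|---|---|---|---|---|
| 0.8 | −60.4% | −61.7% | −62.2% | −68.0% |
| 1.25 | −59.6% | −58.2% | −57.7% | −50.0% |
| 1.5 | −59.2% | −56.6% | −55.7% | −40.0% |
| 2.0 | −58.6% | −54.1% | −52.4% | −20.0% |

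The group columns weight the window values equally and ignore covariate adjustment. They also suppose that the values being replaced would otherwise have left the estimate at −60%.

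**After scaling.** If k is exactly local ULN / central ULN, then local value × (central ULN / local ULN) returns the central value, the shift is zero, and every cell becomes −60%. If the laboratories differ in a way the ULNs do not capture, that part remains.

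**BTH comparison.** Take a participant at a constant multiple of ULN, with two earlier central values and a current local one, and let k be the ratio of the two ULNs. Compared in raw U/L, LDH appears to rise by k − 1: 25%, 50% and 100% for k = 1.25, 1.5 and 2.0. At k = 0.8, a true rise of up to 1/0.8 − 1 = 25% is hidden. Compared as multiples of each laboratory's own ULN, there is no apparent change. For scale, 40 participants followed for 168 days give 40 × 168 / 365.25 = 18.4 patient-years, so one event counted differently moves the rate by 1/18.4, about 0.054 per year.

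**The case against.** The strongest reply is that little rides on this. Row 6.1 is a labelled sensitivity analysis, shown beside a central-only result, so any discrepancy will be seen. Central testing is the default, so few values should be local, and at 5% local the group estimate moves by 0.4 to 1.4 percentage points against a 60% fall. All of that stands and limits the point to a minor specification gap. What it does not answer is attribution: a visible discrepancy still cannot be assigned to missing data or to the laboratory.

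A reader might infer more than the documents support, in four ways.

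- *That the main LDH result is contaminated.* It is not: SAP 2.5 uses central data.
- *That a local baseline distorts the main result.* SAP 2.1.1.2 does say: "If there are no central lab data available, then local lab measurements will be used for baseline computations only". But it gives LDH its own sequence of Day 1 and then screening values, inclusion criterion 4 requires at least two central LDH measurements, and the full analysis set requires confirmed eligibility. The fallback is therefore close to an empty case for LDH.
- *That the substitution in SAP 2.6.3 feeds BTH.* It does not: that section does not list BTH, and the rate is counted from the CRF page.
- *That a switch of laboratory can by itself create a counted BTH.* It cannot. A hemoglobin fall of at least 2 g/dL or significant signs or symptoms is also needed. Nor does Table 8-3 say the comparison is in U/L; an investigator may already be using multiples of ULN, since the same cell sets its threshold that way. This is an ambiguity, not a stated error.

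It is also fair to say that using multiples of ULN for eligibility concedes nothing about mixing laboratories, because eligibility LDH is central only.

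**Conclusion.** The point holds for the LDH sensitivity analysis alone. Local and central U/L are mixed in a ratio to baseline with no scaling, so row 6.1 can reflect the laboratory as well as the missing data it is meant to examine.

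Under an assumed k of 0.8 to 2.0 and a true fall of 60%, the group estimate lies between −60.4% and −58.6% with 5% of window values local, and between −61.7% and −54.1% with 20% local. Individual participants can move much further. Both k and the local share are assumptions, since the documents give neither. The main central-only estimate is unaffected.

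The BTH wording is a lesser, separate ambiguity. It matters only when a clinical criterion is already met, a local result is relied on, and raw units are compared.

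**What to change.** **LDH.** In SAP 2.6.3 and Table 5-1 row 6.1, state that each local LDH is converted to local value × (central ULN / local ULN) before the log ratio is taken. Confirm that the local LDH reference range is captured; the protocol asks for ranges explicitly only for local reticulocyte counts at screening (Sections 3 and 8.1.3). Leave local values without a recorded ULN unsubstituted, and report how many are lost this way.

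The cost is one derivation line and possibly a data query to sites. A few values that this analysis was meant to add may be lost, and the conversion removes only the part of the laboratory difference that the ULN ratio captures.

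**BTH.** For the endpoint derivation, state either that the LDH comparison with the two previous assessments uses multiples of each laboratory's own ULN, or that the paired central value is used when available. If this goes into Table 8-3, it is a protocol amendment needing the approvals in Protocol 14.1. If it goes into SAP 2.6.1.8, the analysis must look at the LDH values behind each CRF-reported event, which the present count does not call for.
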